3.7.7 Columbia Suicide Severity Rating Scale

Response to individual items of C-SSRS as well as the presence (yes or no) of any completed suicide, suicide attempt, preparatory actions towards imminent suicidal behavior, suicidal ideation, and non-suicidal self-injurious behavior at any post-baseline visit will be summarized using number and percentage of subjects for each category.

Table 7. C-SSRS category mapping.

Category	Definition ("Yes" answer to any one of the following)
Completed suicide	Completed Suicide
Suicide attempt	Actual attempt
Preparatory actions towards imminent suicidal behavior	
 • Interrupted attempt • Aborted attempt • Preparatory acts or behavior
Suicide Ideation	
 • Wish to be dead • Non-specific active suicidal thoughts • Active suicidal ideation with any methods (not plan) without intent to act • Active suicidal ideation with some intent to act, without specific plan • Active suicidal ideation with specific plan and intent
Non-suicidal self-injurious behavior	Non-suicidal self-injurious behavior

3.8 PHARMACOKINETIC/PHARMACODYNAMIC DATA ANALYSIS

Subject listings for the concentrations, PK sampling time, and the prior drug dosing time of samidorphan, RDC-9986 (primary metabolite of samidorphan), and olanzapine will be provided.

3.9 INTERIM ANALYSES AND DATA SAFETY MONITORING BOARD

An independent Data Safety Monitoring Board (DSMB) will monitor for tolerability of study drug. Complete details of can be found in DSMB SAP.

3.10 DEVIATIONS FROM THE PROTOCOL AND SPECIFIED ANALYSES

There are no deviations from the protocol specified analyses.

3.11 DEFINITIONS AND CONVENTIONS FOR HANDLING OF DATA

3.11.1 Analysis Visit

Unless otherwise specified, this provides general rules across datasets in ADaMs.

3.11.1.1 Scheduled analysis visit

Scheduled analysis visits are visits upon scheduled time points as specified in the protocol (Table 1 Schedule of Visits and Assessments).

Scheduled analysis visits during the study period will be the same as the nominal visits collected in eCRF. There would be one valid value of assessment kept for each scheduled analysis visit in summary/analysis statistics.

The scheduled repeat measurements at the same visit will be handled as described in SAP Section 3.1.

3.11.1.2 Unscheduled visit

Unscheduled visits are visits with data not collected on the scheduled time point. Unscheduled visits will not be used for by-visit summary/analysis statistics unless specified otherwise.

All unscheduled visits will be included as collected in eCRF in listings.

3.11.1.3 Early termination (ET) visit

An early termination (ET) visit can be mapped to a scheduled visit and be used for analysis and summaries only if there is no valid value already at the mapped visit.

A mapped ET visit will be treated as a scheduled visit to be included in table summaries. Otherwise, it will be treated as an unscheduled visit.

Two rules will be used to map an ET visit.

First, a 7-day (inclusive) window (\leq last dose date + 7) will be used to determine if the assessment at the ET visit is considered to be an on-treatment result. If an ET visit is within 7 days after the last dose of samidorphan/placebo, it will be considered as a valid on-treatment

visit.

Second, visit windows (inpatient stay is excluded) will be applied to determine to which visit an ET valid on-treatment assessment can be mapped to. Visit windows are defined in Table 8 below.

If a subject didn't complete the Part A, his/her ET assessment will not be mapped to Part B visits, i.e. Visit 14 to 23.

Table 8: Visit Window Definition

Analysis Visit to be Mapped to	Target Study Day	Visit Window
Visit 6	15	[9, 18]
Visit 7	22	[19, 25]
Visit 8	29	[26, 32]
Visit 9	36	[33, 43]
Visit 10	50	[44, 57]
Visit 11	64	[58, 71]
Visit 12	78	[72, 85]
Visit 13	92	[86, 98]
Visit 16	99	[99, 102]
Visit 17	106	[103, 109]
Visit 18	113	[110, 116]
Visit 19	120	[117, 127]
Visit 20	134	[128, 141]
Visit 21	148	[142, 155]
Visit 22	162	[156, 169]
Visit 23	176	[170, 183]

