7.3. Subject Withdrawal

A subject may be discontinued from the study at any time if the subject, PI (or designee), or sponsor determines that it is not in the best interest of the subject to continue participation. If a subject has an $ANC < 1.0 \times 10^3$ per μL at anytime from Visit 2 to Visit 25, the PI (or designee) should discontinue the subject from participation immediately.

If a subject withdraws from the study for any reason, any ongoing AEs and/or a low ANC will be followed until resolution, until deemed stable by the PI, or until the subject is deemed by the PI to be lost to follow-up. If, in the opinion of the PI, it is necessary to monitor a subject beyond the

safety follow-up visit, the follow-up period may be extended as necessary. In such instances, the sponsor and the PI will agree to an acceptable follow-up schedule.

In the event that a subject chooses to withdraw from the study, the PI (or designee) should make a reasonable effort to ascertain the reason(s) for withdrawal while fully respecting the subject's rights. The subject should complete an ET visit when possible and subjects should be encouraged to return for follow-up visits 2 and 4 weeks after the ET visit. If the subject fails or refuses to return to the study center, an attempt must be made to contact the subject by telephone in order to assess as many safety and efficacy parameters as possible. All data collected over the telephone must be documented and kept in the subject's record.

The PI must maintain a record of all subjects who fail to complete the study. A full explanation of the reason for study discontinuation will be made on the appropriate electronic case report form (eCRF). If a subject is lost to follow-up, a reasonable attempt to contact the subject must be made and documented.

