8.2. Schedule of Visits and Assessments

The schedule of visits and assessments for Part A is shown in [Table 1](#). The schedule of visits and assessments for Part B is shown in [Table 2](#).

Because fasting glucose and insulin levels will be measured at some visits, subjects will be instructed not to eat or drink for 8 hours before these visits: Visit 2, Visit 3, Visit 13, and Visit 23/ET (see [Table 1](#) and [Table 2](#)). Random glucose and insulin levels will be measured at visits where glucose and insulin measurements are indicated, but fasting is not required.

For a missed visit, the site should attempt to contact the subject to reschedule.

Premature discontinuation procedures are provided in [Section 7.3](#).

Figure 1: Study Design Schematic

[figure not shown]

Table 1: Schedule of Assessments (Part A)

	Screening	Olanzapine	Double-Blind Placebo-Controlled Treatment Period										Transition ¹
	Outpatient Visits		Inpatient Stay			Outpatient Visits						Inpatient Stay ²	
Study Visit	1	2	3	4	5	6	7	8	9	10	11	12	13
Study Day	-30 to -1	1	8 (±1)	9 (±1)	10 (±1)	15 (±1)	22 (±2)	29 (±2)	36 (±2)	50 (±2)	64 (±2)	78 (±2)	92 (±2)
Study Week			1			2	3	4	5	7	9	11	13
Informed Consent	X												
Demographics, Medical/Psychiatric History	X												
Height, Weight, and Waist Circumference ³	X	X	X	X	X	X	X	X	X	X	X	X	X
Pregnancy Test ⁴	X	X											X
Drug Screens ⁵	X	X	X	X	X	X	X	X	X	X	X	X	X
Timeline Follow-Back (TLFB) ⁶	X	X								X			X
Vital Signs ⁷	X	X	X ⁸	X ⁸	X ⁸	X ⁸	X	X	X	X	X	X	X ⁸
Blood and urine samples for clinical labs ⁹	X	X	X		X	X			X		X		X
Hemoglobin A1c, C-reactive protein, leptin	X	X	X								X		X
Carbohydrate Deficient Transferrin (CDT)	X	X									X		X
Electrocardiogram (ECG) ¹⁰	X	X ¹¹	X		X	X							X
Physical Examination ¹²	X	X	X										X
Columbia Suicide Severity Rating Scale (C-SSRS) ¹³	X	X	X	X	X	X	X	X	X	X	X	X	X

	Screening	Olanzapine	Double-Blind Placebo-Controlled Treatment Period										Transition ¹
	Outpatient Visits		Inpatient Stay			Outpatient Visits						Inpatient Stay ²	
Study Visit	1	2	3	4	5	6	7	8	9	10	11	12	13
Study Day	-30 to -1	1	8 (±1)	9 (±1)	10 (±1)	15 (±1)	22 (±2)	29 (±2)	36 (±2)	50 (±2)	64 (±2)	78 (±2)	92 (±2)
Study Week			1			2	3	4	5	7	9	11	13
Positive and Negative Syndrome Scale (PANSS)	X	X	X			X	X		X		X		X
Clinical Global Impressions-Severity (CGI-S)	X	X	X			X	X		X		X		X
Eligibility Criteria Review	X	X	X										
Randomization			X										
Dispense Emergency Treatment Card					X								

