¹² Full physical examination at screening; brief physical examination at all other scheduled time points

¹³ At screening, the "Baseline" version will be administered, and at all other visits the "Since Last Visit" version will be administered.

¹⁴ During inpatient visits, study drug will be administered by the study staff. Otherwise, study drug will be dispensed for self-administration by the subject

Table 2: Schedule of Assessments (Part B)

	Transition ¹			Active ALKS 3831 Treatment Period									Follow-Up	
	Inpatient Stay			Outpatient Visits										
Study Visit	13 ²	14	15	16	17	18	19	20	21	22	23/ET	24	25	
Study Day:	92 (±2)	93 (±2)	94 (±2)	99 (±1)	106 (±2)	113 (±2)	120 (±2)	134 (±2)	148 (±2)	162 (±2)	176 (±2)	190 (±2)	204 (±2)	
Study Week	13			14	15	16	17	19	21	23	25	27	29	
Weight and Waist Circumference	X	X	X	X	X	X	X	X	X	X	X	X	X	
Pregnancy Test ³	X													
Drug Screens ⁴	X		X	X	X	X	X	X	X	X	X	X	X	
Timeline Follow-Back (TLFB) ⁵	X							X			X		X	
Vital Signs ⁶	X ⁷	X ⁷	X ⁷	X ⁷	X	X	X	X	X	X	X	X	X	
Blood and urine samples for clinical labs ⁸	X		X	X			X		X		X		X	
Hemoglobin A1c, C-reactive protein, leptin	X								X		X		X	
Carbohydrate Deficient Transferrin (CDT)	X							X			X			
Blood samples for PK	X	X	X	X	X	X	X	X	X	X	X			
Physical Examination	X				X						X	X	X	
Electrocardiogram (ECG) ⁹	X		X	X							X	X		
Positive and Negative Syndrome Scale (PANSS)	X			X			X		X		X			
Personal and Social Performance Scale (PSP)	X							X			X			

	Transition ¹			Active ALKS 3831 Treatment Period									Follow-Up	
	Inpatient Stay			Outpatient Visits										
Study Visit	13 ²	14	15	16	17	18	19	20	21	22	23/ET	24	25	
Study Day:	92 (±2)	93 (±2)	94 (±2)	99 (±1)	106 (±2)	113 (±2)	120 (±2)	134 (±2)	148 (±2)	162 (±2)	176 (±2)	190 (±2)	204 (±2)	
Study Week	13			14	15	16	17	19	21	23	25	27	29	
Columbia Suicide Severity Rating Scale (C-SSRS)	X	X	X	X	X	X	X	X	X	X	X	X	X	
Clinical Global Impressions-Severity (CGI S)	X			X			X		X		X			
Food Craving Inventory (FCI)	X			X	X						X		X	
Impact of Weight on Quality of Life – Lite Questionnaire (IWQOL-Lite)	X							X			X			
Interactive Web Response System (IWRS)	X	X	X	X	X	X	X	X	X	X	X			
Olanzapine Dosing ¹⁰	X	X	X	X	X	X	X	X	X	X	X	X	X	
Samidorphan Dosing ¹¹	X	X	X	X	X	X	X	X	X	X				
Collect Emergency Treatment Card											X			
Adverse Event (AE) Monitoring	X	X	X	X	X	X	X	X	X	X	X	X	X	
Concomitant Medication Review	X	X	X	X	X	X	X	X	X	X	X	X	X	

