3.6 EFFICACY ANALYSIS

3.6.1 Change in PANSS total Score

The primary endpoint is the change in PANSS total score from randomization to Day 92 and will be evaluated by treatment group (ALKS 3831 pooled vs. the placebo group [olanzapine alone]) using a 2-sided mixed-model for repeated measures (MMRM) to test for equivalence at an alpha level of 0.05. The primary analysis will be conducted in the FAS 1 population.

The null hypothesis is that the PANSS total score change from randomization to Day 92 of ALKS 3831 treatment group will be different to that of the placebo group [olanzapine alone]. The bound of the 2-sided 95% CIs of the difference between the changes of ALKS 3831 – Placebo [olanzapine alone] will be outside the equivalence interval of -10 and 10.

If this analysis shows equivalence, similar analyses on individual dose levels will be performed.

Change in PANSS total score from baseline to Day 92 will be analyzed using MMRM model. The MMRM model will include variables for weight change strata in the olanzapine lead-in period, treatment group, visit, and treatment group-by-visit interaction term as categorical fixed effect, baseline value will be included as a covariate. An AR(1) covariance structure will be

applied for the MMRM. The Kenward-Roger approximation [2] will be used to adjust the denominator degree of freedom. The analysis will be performed on all observed post-randomization scores without imputation of missing data.

A sample of SAS implementation code for analyzing change from randomization to Day 92 using an MMRM is given below.

```
proc mixed data=datain;  
class strata usubjid trt visit;  
  model change = strata trt visit trt*visit base  
    / DDFM=KENWARDROGER;  
repeated visit/ type=AR(1) subject=usubjid;  
lsmeans trt*visit / diff cl;  
run;
```

The least squares (LS) mean, standard error (SE), and LS mean difference between pooled ALKS 3831 treatment group and placebo [olanzapine alone], as well as between each ALKS 3831 treatment group and the placebo [olanzapine alone] at Day 92, along with the 95% CI, will be summarized.

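### SAP Table 8 maps some early-termination PANSS and CGI-S scores to Visits 8, 10 and 12, where neither scale is scheduled, so they have no net weight in the Day 92 MMRM; the effect is modest and the fix cheap

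*SAP*

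**What the plan says.** SAP 3.11.1 introduces the visit rules with "Unless otherwise specified, this provides general rules across datasets in ADaMs", and no exception for a particular scale follows. Under 3.11.1.3 an ET assessment within 7 days of the last samidorphan or placebo dose counts as on-treatment, and then "visit windows (inpatient stay is excluded) will be applied to determine to which visit an ET valid on-treatment assessment can be mapped to". The mapped value can "be used for analysis and summaries only if there is no valid value already at the mapped visit"; otherwise the ET visit is treated as unscheduled, and 3.11.1.2 keeps unscheduled visits out of by-visit analyses unless stated otherwise. For a subject who did not complete Part A, "his/her ET assessment will not be mapped to Part B visits, i.e. Visit 14 to 23". Visit 13, with its window of Days 86-98, therefore remains open to that subject.

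Table 8 includes windows for Visit 8 (Days 26-32), Visit 10 (Days 44-57) and Visit 12 (Days 72-85). After randomization, Protocol Table 1 schedules PANSS and CGI-S in Part A only at Visits 6, 7, 9, 11 and 13.

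On withdrawal, Protocol 7.3 says "The subject should complete an ET visit when possible". Table 1 has no ET column; both scales are marked in the 23/ET column of Table 2.

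The primary PANSS model (SAP 3.6.1) has lead-in weight strata, treatment, visit, treatment-by-visit and baseline, with an AR(1) covariance. The section adds: "The analysis will be performed on all observed post-randomization scores without imputation of missing data". The CGI-S model (3.6.6) has the same mean structure.

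**The concern.** An ET score is often the last on-treatment record of a patient who leaves. The plan labels it valid and then, on some days, files it under a visit where nobody else has that scale. The SAP does not say whether Visits 8, 10 and 12 then become levels of the PANSS and CGI-S models.

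On either reading, the scores from those days cannot, as a group, move the primary PANSS comparison or the secondary CGI-S comparison at Day 92. For PANSS, the LOCF ANCOVA in 3.6.1.1 can still carry them forward. CGI-S has no such second analysis.

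**Working it through.** **Inputs.** From the documents: the Table 8 windows, the Protocol Table 1 schedule and its visit tolerances (Visit 6 ±1 day; Visits 7, 9 and 11 ±2 days), the SAP 3.6.1 model, and 210 pooled ALKS 3831 subjects against 70 on placebo with SD 20 and margin 10. Assumed, because the documents do not give them: Part A dropout, its timing, and the correlation between visits.

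**Plan's own figure.** With no dropout, SE = 20 × √(1/70 + 1/210) = 2.76. Two one-sided tests at 0.05 each give 95.2% power, which matches the stated 95%. The 95% interval rule in 3.6.1 is stricter, but that is a separate matter. This point does not depend on the power figure; the SE only sets the scale.

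**Step 1: classify each possible ET day, Day 9 to Day 98 (90 days), with earlier visits attended on target days.** *Stranded* means mapped to a visit without the scale. *Filled* means the mapped visit already has a value. *Usable* means the score enters at a scheduled PANSS visit.

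| | Table 8 | Windows on Visits 6, 7, 9, 11, 13 only* |
|---|---|---|
| Stranded | 7 + 14 + 14 = 35 | 0 |
| Filled | 3 + 3 + 7 + 7 = 20 | 3 + 7 + 14 + 14 = 38 |
| Usable | 7 + 4 + 4 + 7 + 13 = 35 | 7 + 4 + 7 + 14 + 20 = 52 |

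*Days 9-18, 19-29, 30-50, 51-78 and 79-98.

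Of the 35 stranded days, 17 become usable (30-32, 51-57 and 79-85: 3 + 7 + 7) and 18 become filled (26-29, 44-50 and 72-78: 4 + 7 + 7). If earlier visits fall at the early or late edge of tolerance, Table 8 still strands 35 days, with 27 or 13 filled and 28 or 42 usable. The gain is 17 days each time.

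**Step 2: weight of a stranded score.**

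- *Left out of the MMRM:* the weight is zero.
- *Entered:* in one arm, only ET scores fill the Visit 8 cell (likewise 10 and 12). The model gives that cell its own mean, which appears nowhere else. Adding a constant c to all scores in the cell raises that mean by c and leaves every residual and every other cell mean unchanged, including those at Day 92. The weights of these scores on the Day 92 difference therefore sum to zero, whatever the dropout rate or correlation.

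A numerical check used generalized least squares with the SAP mean model and AR(1), covariance taken as known. It assumed uniform ET days, dropout of 10%, 20% or 30% in both arms or 25% against 10%, lag correlation 0.7-0.95 over eight visit levels, and 0% or 5% missed visits. The stranded ALKS 3831 weights summed to less than 2 × 10⁻¹⁵ in all 1,440 designs. Individual weights are not exactly zero: together they averaged 0.06-0.60% of total absolute weight (largest 1.8%).

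**Step 3: side effect of entering them.** Five visit levels become eight. Under AR(1) on visit order, Visits 7 to 9, 9 to 11 and 11 to 13 change from lag 1 to lag 2 for every subject. In a separate REML simulation with score-related dropout in the ALKS 3831 arm, the fitted correlation per lag rose from about 0.87 to 0.925. The Day 92 estimate differed from simply omitting the scores by 0.05-0.13 points on average (maximum 0.26).

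**Step 4: what scale-specific windows would change.** Under the Step 2 assumptions (lag correlation 0.6-0.9 over five levels), a 10-point shift in the recovered ALKS 3831 scores moves the Day 92 difference by about 0.1-0.7 points. Compared with leaving the stranded scores out, the SE falls by 0.004-0.04 from about 2.8-3.2.

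**Step 5: LOCF.** Under literal Table 8 mapping, ET scores on 35 + 35 = 70 of the 90 days sit at a mapped visit and can be carried forward. With new windows alone this falls to 52, because a score on a filled visit becomes unscheduled. SAP 3.11.2 lets unscheduled values supply the last post-baseline value, but 3.6.1.1 does not say that its LOCF uses that rule.

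**The case against.** The strongest reply is that new windows exchange timing accuracy for use. Every recovered score is assigned to a later visit: Days 30-32 to Visit 9 (4-6 days ahead), Days 51-57 to Visit 11 and Days 79-85 to Visit 13 (both 7-13 days ahead). Seven of the 17 recovered days are thus relabelled as Day 92. This stands as a real cost, close in spirit to carrying a value forward, and it is why Table 8 should remain as a sensitivity mapping. The LOCF loss in Step 5 also stands unless the SAP adds a sentence.

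It is also fair that PANSS and CGI-S at a Part A ET visit are inferred from the Part B table, and that ET visits occur only when possible.

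A reader might infer that the SAP breaks its statement about using all observed scores. The documents do not support that. Section 3.6.1 speaks of using observed scores without imputation and promises no particular weight; on the literal mapping the scores do enter. The leavers' earlier scores at scheduled visits also still inform Day 92.

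**Conclusion.** The mismatch is plain in the documents, and the zero net weight is algebraic. It is a stated rule that works worse than an easy alternative, so it is worth correcting, but it does not threaten the primary analysis. The size, about 0.1-0.7 points for a 10-point shift, rests on assumed dropout, timing and correlation, and is small beside an SE of about 3 and a margin of 10.

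Two stronger conclusions are tempting. One is that 39% (35 of 90) of leavers' scores are lost; that figure counts calendar days, not patients or information. The other is that the Day 92 result is biased in a known direction; the documents give no Part A dropout rate or timing, so neither the size nor the direction of any bias is established.

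**What to change.** Before database lock and unblinding:

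- In SAP 3.11.1.3, add ET windows for PANSS and CGI-S built only on Visits 6, 7, 9, 11 and 13, for example those in the Step 1 table. Keep Table 8 for weight, which is measured at every visit.
- State that Visits 8, 10 and 12 are not levels in the PANSS or CGI-S MMRM.
- In 3.6.1.1, state that the LOCF ANCOVA carries forward the last valid on-treatment value under the 3.11.2 rule, including an ET score whose mapped visit is already filled. No valid on-treatment ET score is then lost from LOCF.
- Optionally keep the Table 8 mapping as a sensitivity analysis.

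The cost is one small table and two sentences, with no new data. In return for the 17 usable days, a used score may sit up to 13 days from its target day (14 if the scheduled visit was missed), against 6 under Table 8 when earlier visits were attended on target. The other 18 stranded days fall on a filled visit and stay out of the MMRM, where the value kept can be 14 days older than the ET score (7 under Table 8).

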
- Olanzapine + Samidorphan (5 mg)
- Olanzapine + Samidorphan (10 mg)
- Olanzapine + Samidorphan (20 mg)
- Olanzapine + Placebo

All study drug will be taken once daily by mouth. Olanzapine and samidorphan/placebo tablets should be taken together (ie, at the same time). Randomization will be stratified by the amount of weight change during the olanzapine lead-in period (ie, from Day 1 to Day 8), with subjects grouped into the following 3 strata:

- Weight change ≤ 0 kg
- Weight increase >0 to <1 kg
- Weight increase ≥ 1 kg

Subjects will be discharged from the inpatient unit on Study Day 10 (Visit 5) and will return on Study Day 15 (Visit 6).

Subjects are not required to be taking any antipsychotic medication at the time of screening or Visit 2. However, those who are will be tapered off of their prior antipsychotic medication within two weeks after initiation (ie, by Study Day 15, Visit 6). This cross-taper from prior antipsychotic treatment to olanzapine will be conducted under the care and discretion of the PI and consistent with current clinical practice.

After Study Day 15 subjects will return to the clinic weekly through the first month of double-blind treatment (ie, Study Day 36) and then every 2 weeks thereafter for the remainder of Part A. Any subject who prematurely discontinues during Part A will be asked to return to the clinic for an early termination (ET) visit and will be asked to return for follow-up visits 2 and 4 weeks later.

Part A Visit Schedule

	Screening	Olanzapine Lead-In	Double-Blind Placebo-Controlled Treatment Period										Transition*
Visit	1	2	3	4	5	6	7	8	9	10	11	12	13
Day	-30 to -1	1	8	9	10	15	22	29	36	50	64	78	92
Week			1			2	3	4	5	7	9	11	13

* Transition (Visit 13) is the end of Part A and the beginning of Part B (Part B begins with dosing at Visit 13). Shaded cells represent inpatient stays.

Assessments prior to study drug administration at Visit 13 (the transition visit) will serve as end of Part A assessments; dosing and post-dose assessments will be considered Part B assessments.

Part B (Active ALKS 3831 Treatment and Safety Follow-up Periods)

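### An early-termination visit between the first Part B dose and Day 98 can map only to Visit 13, the end of Part A, and so usually drops out of the Part B by-visit summaries

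*SAP*

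**What the plan says.** The protocol draws the line between the two parts at the Visit 13 dose. Its synopsis states that "Part B begins with dosing at Visit 13". Assessments before that dose close Part A, while "dosing and post-dose assessments will be considered Part B assessments". At this dose placebo subjects change to samidorphan at the highest dose, and the other arms keep their dose (Protocol 8.1.2).

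SAP 3.11.1.3 maps ET visits in two steps. The visit must be on treatment: "If an ET visit is within 7 days after the last dose of samidorphan/placebo", it qualifies. It is then placed by study day using Table 8, where Visit 13 has Days 86-98 and Visit 16 has Days 99-102. The inpatient Visits 14 and 15 have no window. A mapped ET value is "used for analysis and summaries only if there is no valid value already at the mapped visit". "Otherwise, it will be treated as an unscheduled visit". SAP 3.11.1.2 adds: "Unscheduled visits will not be used for by-visit summary/analysis statistics unless specified otherwise".

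The only guard between the parts concerns subjects who did not complete Part A: "his/her ET assessment will not be mapped to Part B visits, i.e. Visit 14 to 23".

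**The concern.** The guard works in one direction. It keeps Part A terminations out of Part B visits, but nothing keeps a Part B termination out of Visit 13. For an ET visit made after the first Part B dose and by Day 98, there are two outcomes.

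- **Visit 13 has a valid value (the usual case).** The ET assessment becomes unscheduled and leaves the by-visit summaries. PANSS and CGI-S are not scheduled again until Visit 16 (Protocol Table 2), so this is typically the subject's only on-treatment Part B rating on either scale.
- **The measure is missing at Visit 13 (rare).** The post-dose ET value becomes the Day 92 value, which is the time point of the primary PANSS comparison (SAP 3.6.1) and of the weight comparison (SAP 3.6.2). This contradicts the protocol's split. For a placebo subject, the value was obtained on samidorphan.

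**Working it through.** No stated figure has to be reproduced. The check applies the mapping rules day by day.

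**1. Where an ET visit lands (Table 8)**

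| ET study day | Mapped to |
|---|---|
| 93-98 | Visit 13 |
| 99-102 | Visit 16 |
| 103-109 | Visit 17 |

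**2. Length of the overlap.** With Visit 13 on day D, the days after D up to Day 98 number 98 − D. Protocol Table 1 allows Day 92 ±2.

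- D = 90: 98 − 90 = 8 days
- D = 92: 98 − 92 = 6 days
- D = 94: 98 − 94 = 4 days

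The whole Visit 13 window is 98 − 86 + 1 = 13 days.

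**3. On-treatment rule.** At nominal timing the earliest possible last dose in Part B is on Day 92, and 92 + 7 = 99. Every ET visit on Days 93-98 therefore qualifies.

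**4. Visit date, not stopping date.** Take last doses on Days 92-98 and ET visits from Day 93 (and not before the last dose) up to last dose + 7. There are 55 date pairs: 27 fall in the Visit 13 window, 22 in Visit 16 and 6 in Visit 17. These are counts of possible dates, not probabilities. A subject who stops in the first week but attends on Day 99 or later stays in Part B.

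**5. Table 8 against its own pattern.** Of the 15 boundaries between adjacent windows, 14 lie at the midpoint of the two target days. The exception is Visit 13/Visit 16: (92 + 99)/2 = 95.5 would cut after Day 95, but the table cuts after Day 98. The SAP states no midpoint rule, so this is only an observation.

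The first randomized dose gives a closer parallel:

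| | First dose | Inpatient days | Next visit | Its window |
|---|---|---|---|---|
| Part A | Day 8 | 9-10 | Visit 6, Day 15 | 9-18 |
| Part B | Day 92 | 93-94 | Visit 16, Day 99 | 99-102 |

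Visit 6 opens the day after the dose and closes 3 days after its target. The same construction for Visit 16 gives Days 93-102. The parallel is not complete, because no earlier window competes with Visit 6.

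**6. Size, on assumed inputs**

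- *Missing Visit 13 value, placebo arm.* Let one value be wrong by 10-20 points among 55-70 placebo values. The planned arm size is 70; the other figures are assumptions. The simple mean shifts by 10/70 = 0.14 to 20/55 = 0.36 points. The mixed model will not reproduce this exactly.
- *Dropped Part B value.* Let 200 subjects enter Part B and 1-5% have an ET visit in the overlap, which is 2 to 10 subjects. If their PANSS totals were 10-20 points worse, including them would move the Visit 16 mean by 2 × 10/200 = 0.1 to 10 × 20/200 = 1.0 points. That they score worse is also an assumption.

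**The case against.** The strongest reply is that the intent is already clear. The protocol assigns post-dose data to Part B, SAP 3.10 declares no deviations from the protocol's analyses, and the SAP says only that an ET visit can be mapped. That is a fair account of intent. A general statement does not override an explicit window table, however, and a programmer following Table 8 would place these visits at Visit 13.

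The Day 98 limit also has a use. A Part A subject whose last dose was on Day 91 may have an on-treatment ET visit up to Day 98 (91 + 7) and may not be mapped to Part B. This stands, and the window should remain for such subjects.

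A reader might infer that early failures after the switch to samidorphan vanish from Part B. The documents do not support that. These subjects remain in the Part B Safety Population (SAP 3.2.3), in disposition with reasons for discontinuation (3.3) and in the adverse-event summaries (3.7.2). Weight and vital signs recorded at Visits 14 and 15 are nominal scheduled data and are unaffected. The ET values stay in listings and can feed last and any post-baseline derivations (3.11.2, 3.11.3). Nor was the Visit 13 inpatient stay set up to detect PANSS worsening: Protocol 8.1 ties it to somnolence and orthostatic hypotension, which adverse events and the orthostatic measurements at Visits 13-16 capture.

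**Conclusion.** The gap is real and minor. Read literally, the SAP sends every on-treatment ET visit made after the first Part B dose and by Day 98 to Visit 13. The usual result is the loss of one PANSS and one CGI-S rating per affected subject from Part B summaries that are descriptive and carry no hypothesis test.

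A reader might go further and conclude that the primary equivalence result is at risk. It is not, on any plausible count. That path needs a measure missing at an inpatient visit where it is due before dosing, followed by termination within days. Only placebo subjects change treatment there. The assumed shift of 0.1 to 0.4 points per value is small against the 10-point margin.

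The reading of the windows is firm. The sizes are not: the documents give no number of subjects entering Part B, no early termination rate and no count of missing Visit 13 values.

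**What to change.** Add to SAP 3.11.1.3: *An ET assessment made after the first Part B dose will not be mapped to Visit 13 or earlier.*

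In Table 8, for subjects dosed in Part B only, open the Visit 16 window on the day after the first Part B dose and close it on Day 102, in line with the Visit 6 window. Keep Days 86-98 for Visit 13 for subjects who did not enter Part B.

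The cost is one sentence and one table row, settled before unblinding, with no new data. The drawback is that a few ET values from before Day 99 would carry the Visit 16 label, some of them up to 6 days early at nominal timing (99 − 93). A footnote to the table can say so.
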